### 2 PROTOCOL SYNOPSIS

**Title** A Phase 3, Rollover Study to Evaluate the Safety of Long-term Treatment With

Lumacaftor/Ivacaftor Combination Therapy in Subjects Aged 2 Years and Older

With Cystic Fibrosis, Homozygous for the F508del-CFTR Mutation

**Brief Title** A Rollover Safety Study of Lumacaftor/Ivacaftor in Subjects Aged 2 Years and

Older With Cystic Fibrosis, Homozygous for F508del

# Clinical Phase and Clinical Study Type

Phase 3 safety

### **Objectives** Primary Objective

To evaluate the long-term safety of lumacaftor/ivacaftor (LUM/IVA) combination therapy in subjects aged 2 years and older with cystic fibrosis (CF), homozygous for *F508del* 

#### **Secondary Objective**

To evaluate the pharmacodynamics (PD) of long-term LUM/IVA combination therapy in subjects aged 2 years and older with CF, homozygous for *F508del* 

### **Endpoints** Primary Endpoint

Safety and tolerability assessments based on adverse events (AEs), changes in clinical laboratory values, electrocardiograms (ECGs), vital signs, pulse oximetry, ophthalmological examinations (OEs), and spirometry

#### **Secondary Endpoints**

The following endpoints will be analyzed using baseline values in the previous study (i.e., Study VX15-809-115 Part B [Study 115B]):

- Absolute change from baseline in sweat chloride
- Absolute change from baseline in body mass index (BMI) and BMI-for-age z-score
- Absolute change from baseline in weight and weight-for-age z-score
- Absolute change from baseline in stature and stature-for-age z-score
- Time-to-first pulmonary exacerbation from baseline
- Number of pulmonary exacerbations from baseline
- Number of CF-related hospitalizations from baseline
- Absolute change from baseline in fecal elastase-1 (FE-1) levels
- Absolute change from baseline in serum levels of immunoreactive trypsinogen (IRT)
- Change from baseline in microbiology cultures
- Absolute change from baseline in lung clearance index (LCI)2.5
- Absolute change from baseline in LCI50

#### **Number of Subjects** Approximately 56 subjects are potentially eligible to be enrolled

#### Study Population Treatment Cohort

Male and female subjects who completed LUM/IVA treatment and the Safety Follow-up Visit in Study 115B

#### Observational Cohort

Male and female subjects who received at least 4 weeks of LUM/IVA treatment in Study 115B and completed visits up to Week 24 and the Safety Follow-up Visit, if required, in Study 115B, but do not meet eligibility criteria for enrollment in the Treatment Cohort or who choose not to enroll in the Treatment Cohort

#### **Investigational Drug**

Active Substance: LUM/IVA fixed-dose combination

**Activity:** CFTR corrector and potentiator (chloride ion [Cl] secretion)

#### Strength and Route of Administration

- LUM 100-mg/IVA 125-mg granules for oral administration
- LUM 150-mg/IVA 188-mg granules for oral administration
- LUM 100-mg/IVA 125-mg tablets for oral administration

#### **Doses Investigated**

### Subjects 2 through 5 years of age at enrollment

- LUM 100 mg/IVA 125 mg every 12 hours (q12h) for subjects weighing
   4 kg at enrollment
- LUM 150 mg/IVA 188 mg q12h for subjects weighing ≥14 kg at enrollment

Notes: Doses may be adjusted upward for changes in weight and age. Doses above are those planned for Study 115B. Based on results from Study 115A and 115B, doses for subjects <6 years of age in Study VX16-809-116 (Study 116) may be modified.

### Subjects ≥6 years of age at enrollment

LUM 200 mg/IVA 250 mg q12h (2 × LUM 100-mg/IVA 125-mg tablet q12h)

#### Study Duration

#### **Treatment Cohort**

Up to 98 weeks (96 weeks for the Treatment Period and 2 weeks for safety follow-up, if applicable)

### Observational Cohort

96 weeks

### **Study Design**

The Treatment Cohort includes the following:

- Treatment Period (Day 1 through Week 96; the last dose of study drug is the dose before the Week 96 Visit).
- Safety Follow-up Visit (2 weeks  $\pm$  4 days after the last dose of LUM/IVA)

The Observational Cohort includes 2 long-term follow-up telephone contacts at Week 48 and Week 96.

#### **Assessments**

#### Treatment Cohort

Safety: AEs, clinical laboratory values (serum chemistry, hematology, coagulation, and urinalysis), ECGs, vital signs, pulse oximetry, physical examinations, spirometry (subjects ≥3 years old at screening in Study 115B), and OEs

Pharmacodynamics: Sweat chloride, BMI/BMI-for-age z-score, weight/weight-for-age z-score, stature/stature-for-age z-score, spirometry (subjects ≥3 years old at screening in Study 115B), pulmonary exacerbations, CF-related hospitalizations, FE-1, IRT, qualitative microbiology cultures, and LCI (subjects ≥3 years old at screening in Study 115B who consent/assent to the optional LCI Substudy in Study 115B and Study 116)

#### Observational Cohort

Safety: Serious adverse events (SAEs)

#### **Statistical Analyses**

Approximately 56 subjects are potentially eligible to be enrolled. Assuming a 10% dropout rate in Study 115B, 50 subjects are expected to be enrolled in Study 116.

#### Treatment Cohort

The analysis will be performed over the Cumulative Study Period.

#### **Safety Analysis**

All treatment-emergent AE (TEAE) summaries will be described using the incidence of TEAEs and number of events per 100 patient-years (number of events adjusted for the total duration of exposure) for the Cumulative Study Period.

Continuous safety endpoints will be summarized descriptively at each visit during the Cumulative Study Period.

For the categorical laboratory, vital, and ECG variables, the number and percentage of subjects in each category during the Treatment-emergent Period of the Cumulative Study Period will be summarized.

The safety analysis for the Cumulative Study Period will be based on the Safety Set, which will include all subjects who received at least 1 dose of study drug in Study 115B.

#### Pharmacodynamic Analysis

For all continuous PD endpoints, raw values and absolute change from Cumulative Study Baseline at each visit in the Cumulative Study Period will be summarized based on the Full Analysis Set (FAS), which includes all subjects who were enrolled and exposed to any amount of study drug in Study 115B.

Time-to-first pulmonary exacerbation will be estimated using the Kaplan-Meier method based on the FAS for the Cumulative Study Period.

The number of pulmonary exacerbations starting during the Cumulative Study Period normalized by the time spent in the Cumulative Study Period will be summarized.

The number of CF-related hospitalizations through last visit will be summarized similarly.

#### Observational Cohort

Listings will be provided for SAEs in Study 116 based on all subjects enrolled in the Observational Cohort.

### **IDMC Reviews**

An independent data monitoring committee (IDMC) will be formed using the Cystic Fibrosis Foundation Data Safety Monitoring Board. The IDMC objectives and operational details will be defined in a separate document (IDMC Charter), which will be finalized before the first subject is enrolled. The IDMC will conduct regular planned reviews of study data for the purpose of safety monitoring as outlined in the IDMC Charter.

#### 3 SCHEDULE OF ASSESSMENTS

### 3.1 Treatment Cohort

Table 3-1 Study VX16-809-116: Treatment Cohort - Treatment Period and Safety Follow-up Visit

		Treatment Period					Safety Follow-up Visit c
Event/Assessment a	Day 1 d	Day 3 (± 1 Day)	Day 15 (± 3 Days)	Weeks 12, 24, 36, 48, 60, 72, 84 (± 7 Days)	Week 96 (± 7 Days)	As Soon as Possible After the Last Dose	2 Weeks (± 4 Days) After the Last Dose
Informed consent/assent	X						
Clinic visit	X		X	X	X	X	X
Telephone contact e		X					
Stature and weight f	X		X	X	X	X	X
Vital signs g	$X^{h}$		X	X	X	X	X
Pulse oximetry g	X		X	X	X	X	X
OEs i	X			Week 48 j	$X^{j,k}$	$X^{j,k}$	$X^{j,k}$
Full PE 	X			Weeks 24, 48, 72	X	X	X
Abbreviated PE	X m						

- a Assessments will be performed before LUM/IVA dosing unless noted otherwise.
- b If the ETT Visit occurs 10 days or later after the last dose of LUM/IVA, the Safety Follow-up Visit will not be required (Section 9.1.2.3). Subjects who prematurely discontinue LUM/IVA treatment for AEs should be followed until the AE is considered resolved.
- The Safety Follow-up Visit is required for 1) subjects who complete their ETT Visit <10 days after the last dose of LUM/IVA (footnote b and Section 9.1.2.3); and 2) subjects who interrupt LUM/IVA treatment and complete their Week 96 Visit <10 days after the last dose of LUM/IVA; it is not required for subjects who continue onto commercially-available, physician-prescribed LUM/IVA within 2 weeks (± 4 days) of completing LUM/IVA treatment at the Week 96 or ETT Visit.
- For subjects at sites activated by the time of their Study 115B Safety Follow-up Visit, their Study 116 Day 1 Visit will be on the same day as their Study 115B Safety Follow-up Visit, and any Study 116 Day 1 assessments that were specified to be performed at the Study 115B Safety Follow-up Visit does not coincide with the subject's Study 115B Safety Follow-up Visit, the subject will complete all Study 116 Day 1 assessments (except the OE if it was performed within the last 3 months before the visit). See Section 9.1.1 for details.
- e Telephone contacts will be made to assess the subject's status, any AEs, medications, treatments, and procedures.
- If subjects can stand unassisted and follow directions, stature should be measured as height; otherwise, stature will be measured as length. Stature and weight must be measured with shoes off and while wearing light clothing. BMI will be derived from this assessment. See Section 11.4.3 for details.
- The subject should rest for at least 5 minutes before having vital signs and pulse oximetry measured. See Section 11.6.4 for details.
- h Vital signs will be measured predose and at 1 hour (± 15 minutes), 2 hours (± 15 minutes), and 4 hours (± 15 minutes) postdose on Day 1.
- An OE will be conducted by a licensed ophthalmologist. Subjects with documentation of bilateral lens removal do not need the OE. See Section 11.6.6 for details.
- Subjects may complete the OE within  $\pm 1$  week of the scheduled visit.
- An OE will be conducted at the Week 96 Visit (or the ETT Visit if the subject does not have a Week 96 Visit, unless the discontinuation is due to initiation of treatment with commercially-available LUM/IVA), or the Safety Follow-up Visit.
- Symptom-directed PEs will occur at any time during the study if triggered by AEs or if deemed necessary by the investigator. See Section 11.6.4 for details.
- m An abbreviated PE will be performed 4 hours (± 30 minutes) postdose on Day 1. See Section 11.6.4 for details.

Table 3-1 Study VX16-809-116: Treatment Cohort - Treatment Period and Safety Follow-up Visit

	Treatment Period				ETT Visit b	Safety Follow-up Visit c	
Event/Assessment a	Day 1 d	Day 3 (± 1 Day)	Day 15 (± 3 Days)	Weeks 12, 24, 36, 48, 60, 72, 84 (± 7 Days)	Week 96 (± 7 Days)	As Soon as Possible After the Last Dose	2 Weeks (± 4 Days) After the Last Dose
Standard 12-lead ECGs n	X		X	Week 48	X	X	X
Serum chemistry o	X		X	Weeks 12, 24, 36, 48, 72	X	X	X
Hematology o				Weeks 12, 24, 36, 48, 72	X	X	X
Coagulation studies o				Week 48	X		
Urinalysis o	X			Week 48	X		
Qualitative microbiology cultures p	X			Weeks 24, 48, 72	X	X	
Immunoreactive trypsinogen	X			Week 48	X		X
Fecal elastase-1 q	X			Week 48	X		X
Sweat chloride r	X			Weeks 24, 48	X		X
LCI (optional) s	X			Weeks 24, 48	X		X
Spirometry t	X u		X	Weeks 24, 48	X	X	X
Other events related to outcome v	X		X	X	X	X	X
LUM/IVA dosing w							
Observation 4 hours after the first dose	X						
Study drug count	X		X	X	X	X	

A standard 12-lead ECG will be performed. The subject will be instructed to rest in the supine position for at least 5 minutes, if possible, before having an ECG performed. The ECG will be performed before any other procedures that may affect heart rate, such as blood draws. See Section 11.6.5 for details.

<sup>o See Section 11.6.2 for details.

<sup>p See Section 11.4.7 for details.

<sup>q Samples will be collected at the study center during the study visit; however, samples may be collected by the subject up to 24 hours before the study visit (e.g., at home) and brought to the study visit (Section 11.4.5). The sample may be collected pre- or postdose.

The sweat chloride test will be conducted at approximately the same time as predose blood collections. At each time point, 2 samples will be collected, 1 sample from each arm (left and right). See Section 11.4.1 for details.

The LCI assessment (only subjects who are  $\ge 3$  years of age at Study 115B screening who consent/assent to the optional LCI Substudy in Study 115B and Study 116) should be performed pre-bronchodilator. See Sections 11.1 and 11.4.2 for details. The assessment will be performed in multiple replicates and before the spirometry assessment.

<sup>t Spirometry (only subjects who are ≥3 years of age at Study 115B screening) should be performed pre-bronchodilator. See Sections 11.1 and 11.6.7 for details.

Day 1 spirometry will be performed before LUM/IVA dosing and at 2 hours (± 30 minutes) and 4 hours (± 30 minutes) postdose.

Other events related to outcome include assessments relating to pulmonary exacerbations, administration of antibiotic therapy for sinopulmonary signs or symptoms, and hospitalizations (Section 11.4.4).

W LUM/IVA will be administered q12h (± 2 hours) within 30 minutes of consuming fat containing food (Section 9.6). On days of scheduled visits, the dose will be administered at the site after predose assessments have been completed. The last dose will be the dose administered before the Week 96 Visit. See Section 9.6 for dose determination details.

Table 3-1 Study VX16-809-116: Treatment Cohort - Treatment Period and Safety Follow-up Visit

			Treatm	ent Period		ETT Visit b	Safety Follow-up Visit c	
Event/Assessment a	Day 1 d	Day 3 (± 1 Day)	Day 15 (± 3 Days)	Weeks 12, 24, 36, 48, 60, 72, 84 (± 7 Days)	Week 96 (± 7 Days)	As Soon as Possible After the Last Dose	2 Weeks (± 4 Days) After the Last Dose	
Medications, treatments, and		Continuous from signing of ICE through Sofety Follow, un Visit (if required)						
Adverse events		Continuous from signing of ICF through Safety Follow-up Visit (if required)  Continuous from signing of ICF through Safety Follow-up Visit (if required)						

AE: adverse event; BMI: body mass index; ECG: electrocardiogram; ETT: Early Termination of Treatment; ICF: informed consent form; IVA: ivacaftor; LCI: lung clearance index; LUM: lumacaftor; OE: ophthalmological examination; PE: physical examination; q12h: every 12 hours

### 3.2 Observational Cohort

Table 3-2 Study VX16-809-116: Observational Cohort

Event/Assessment	Day 1 a	Long-term Follow-up Telephone Contact Weeks 48 and 96 (± 4 weeks)	Early Termination Telephone Contact b			
Informed consent/assent	X					
Clinic visit	X					
Telephone contact		X	X			
Serious adverse events	Continu	nuous from signing of ICF through Week 96 or Early Termination Telephone				
		Contact				

ICF: informed consent form; IVA: ivacaftor; LUM: lumacaftor

For subjects at sites activated by the time of their applicable Study 115B visit (i.e., the Week 24 Visit or the Safety Follow-up Visit, if required), their Study 116 Day 1 Visit will be the same day as their applicable Study 115B visit, and any Study 116 Day 1 assessments that were specified to be performed at the applicable Study 115B visit do not need to be repeated. If the Study 116 Day 1 Visit does not coincide with the subject's applicable Study 115B visit, the subject will complete all Study 116 Day 1 assessments. See Section 9.1.1 for details.

Subjects who become eligible to receive commercially-available, physician-prescribed LUM/IVA, and who choose to continue onto commercially-available LUM/IVA, must have an Early Termination Telephone Contact to terminate study participation.

# **List of Abbreviations**

Abbreviation	Definition
AE	adverse event
ALP	alkaline phosphatase
ALT	alanine aminotransferase
AST	aspartate aminotransferase
ATC	anatomic class
BMI	body mass index
CF	cystic fibrosis
CFTR	CF transmembrane conductance regulator gene
CFTR	CF transmembrane conductance regulator protein
CI	confidence interval
Cl 	chloride ion
CRF	case report form
CTCAE	Common Terminology Criteria for Adverse Events
CYP	cytochrome P450
ECG	electrocardiogram
EDC	electronic data capture
EENT	eyes, ears, nose, and throat
ETT	early termination of treatment
EU	European Union
F508del	CFTR gene mutation with an in-frame deletion of a phenylalanine codon corresponding to position 508 of the wild-type protein
F508del	CFTR protein lacking the phenylalanine normally found at position 508 of the wild-type protein
FAS	Full Analysis Set
FDA	Food and Drug Administration
FE-1	fecal elastase-1
FEF 25-75%	forced expiratory flow, midexpiratory phase
$FEV_1$	forced expiratory volume in 1 second
FVC	forced vital capacity
GCP	Good Clinical Practice
GGT	gamma-glutamyl transferase
GLI	Global Lung Function Initiative
GPS	Global Patient Safety
HIPAA	Health Insurance Portability and Accountability Act
HR	heart rate
ICF	informed consent form
ICH	International Conference on Harmonization
IDMC	independent data monitoring committee
IEC	independent ethics committee
IRB	institutional review board
IRT	immunoreactive trypsinogen
IV	intravenous
IVA	ivacaftor
LCI	lung clearance index

Abbreviation	Definition
LCI 25	number of lung turnovers required to reduce the end tidal inert gas concentration to 1/40th of its starting value
LCI 50	number of lung turnovers required to reduce the end tidal inert gas concentration to 1/20th of its starting value
LFT	liver function test
LLN	lower limit of normal
LUM	lumacaftor
MBW	multiple-breath washout
MedDRA	Medical Dictionary for Regulatory Activities
OE	ophthalmological examination
P	probability
PD	pharmacodynamics(s)
PE	physical examination
PK	pharmacokinetic(s)
$ppFEV_1$	percent predicted FEV 1
PR	PR interval
PT	preferred term
q12h	every 12 hours
QRS	the portion of an ECG comprising the Q, R, and S waves, together representing ventricular depolarization
QT	QT interval
QTc	QT interval corrected
QTcF	QT interval corrected by Fridericia's formula
RR	interval from the onset of 1 QRS complex to the next
SAE	serious adverse event
SAP	statistical analysis plan
SD	standard deviation
SE	standard error
SI	SI units (International System of Units)
SOC	system organ class
SUSAR	suspected, unexpected, serious adverse reaction
TEAE	treatment-emergent adverse event
ULN	upper limit of normal
US	United States

### 5 INTRODUCTION

### 5.1 Background

Cystic fibrosis (CF) is an autosomal recessive disease with serious, chronically debilitating morbidities and high premature mortality and at present, there is no cure. CF affects approximately 70,000 individuals worldwide, with approximately 30,000 individuals in the US. Despite progress in the treatment of CF with antibiotics and mucolytics, the predicted median age of survival for a person with CF is approximately 40 years. Although the disease affects multiple organs, progressive loss of lung function is the leading cause of mortality.

CF is caused by a defect in the gene encoding CFTR, an epithelial chloride (Cl) ion channel that is responsible for aiding in the regulation of salt and water absorption and secretion in various tissues. This function is defective in patients with CF due to a loss of cell surface expression and/or function of CFTR.

Lumacaftor (LUM; VX-809)/ivacaftor (IVA; VX-770) combination therapy (OrkambiTM) is the first medicine designed to treat the underlying molecular defect and enhance the function of CFTR in patients homozygous for *F508del*. Orkambi is approved in the US for patients 6 years and older who are homozygous for *F508del*, and in the EU, Canada, Australia, and Switzerland for patients 12 years and older who are homozygous for *F508del*. The LUM/IVA development program is designed to support the hypothesis that an oral chronic treatment restoring CFTR function can lead to improved pulmonary and extrapulmonary manifestations of CF, prevent progressive lung damage, and ultimately prolong survival.

Details about the LUM/IVA development program can be found in the Investigator's Brochure.

## 5.2 Study Rationale

Approximately half of the total CF patient population is <18 years of age. Even before the widespread adoption of newborn screening, the majority of patients with CF were diagnosed in infancy or early childhood due to manifestations of the disease. Pancreatic destruction leading to pancreatic exocrine insufficiency begins in utero, and lung involvement is manifest by pulmonary inflammation and infection that begins shortly after birth.

The primary objectives of Study VX15-809-115 (Study 115) are to obtain pharmacokinetic (PK) and safety information to support a proposed indication expansion of LUM/IVA in subjects aged 2 through 5 years, homozygous for *F508del*. The primary objective of Study VX16-809-116 (Study 116) is to evaluate the long-term safety of LUM/IVA in subjects aged 2 years and older with CF, homozygous for *F508del*, who participated in Study 115.

#### 6 STUDY OBJECTIVES

### **6.1** Primary Objective

To evaluate the long-term safety of LUM/IVA combination therapy in subjects aged 2 years and older with CF, homozygous for F508del

### **6.2** Secondary Objective

To evaluate the pharmacodynamics (PD) of long-term LUM/IVA combination therapy in subjects aged 2 years and older with CF, homozygous for *F508del* 

#### 7 STUDY ENDPOINTS

### 7.1 Primary Endpoint

Safety and tolerability assessments based on adverse events (AEs), changes in clinical laboratory values, electrocardiograms (ECGs), vital signs, pulse oximetry, ophthalmological examinations (OEs), and spirometry

### 7.2 Secondary Endpoints

The following endpoints will be analyzed using baseline values in the previous study (i.e., Study 115 Part B [Study 115B]):

- Absolute change from baseline in sweat chloride
- Absolute change from baseline in body mass index (BMI) and BMI-for-age z-score
- Absolute change from baseline in weight and weight-for-age z-score
- Absolute change from baseline in stature and stature-for-age z-score
- Time-to-first pulmonary exacerbation from baseline
- Number of pulmonary exacerbations from baseline
- Number of CF-related hospitalizations from baseline
- Absolute change from baseline in fecal elastase-1 (FE-1) levels
- Absolute change from baseline in serum levels of immunoreactive trypsinogen (IRT)
- Change from baseline in microbiology cultures
- Absolute change from baseline in lung clearance index (LCI)2.5
- Absolute change from baseline in LCI5.0

#### 8 STUDY POPULATION

Eligibility will be reviewed and documented by an appropriately qualified member of the investigator's team before subjects are enrolled.

Subjects who meet all of the inclusion criteria and none of the exclusion criteria will be eligible for the study.

#### 8.1 Inclusion Criteria

1. Subject's legally appointed and authorized representative (e.g., parent or legal guardian) will sign and date an informed consent form (ICF) and the subject will sign and date an assent form (if applicable).

- 2. Subjects entering the **Treatment Cohort** must meet the following criteria:
  - Completed 24 weeks of LUM/IVA treatment and the Safety Follow-up Visit in Study 115B
    - Subjects who had study drug interruptions are eligible if they completed study visits up to the Safety Follow-up Visit of Study 115B. Subjects who are not taking LUM/IVA at the end of the Study 115B Treatment Period (i.e., Week 24), including subjects who have LUM/IVA treatment temporarily interrupted as of Day 1 in Study 116, must receive Vertex approval for enrollment in the Treatment Cohort.

Subjects entering the **Observational Cohort** must meet 1 of the following criteria:

- Completed 24 weeks of LUM/IVA treatment and the Safety Follow-up Visit in Study 115B, but do not want to enroll in the Treatment Cohort.
- Received at least 4 weeks of LUM/IVA treatment and completed visits up to Week 24 and the Safety Follow-up Visit, if required, of Study 115B but are not taking LUM/IVA at the end of the Study 115B Treatment Period (i.e., Week 24) because of a drug interruption and either did not receive Vertex approval to enroll in the Treatment Cohort or do not want to enroll in the Treatment Cohort.
- Permanently discontinued LUM/IVA in Study 115B after receiving at least 4 weeks of treatment and remained in the study from the time of treatment discontinuation through the Week 24 Visit and Safety Follow-up Visit, if required.
- 3. Willing to remain on a stable CF medication regimen through the Safety Follow-up Visit (Treatment Cohort only).
- 4. As deemed by the investigator, the subject's legally appointed and authorized representative (e.g., parent or legal guardian) must be able to understand protocol requirements, restrictions, and instructions. The subject's legally appointed and authorized representative should be able to ensure that the subject will comply with, and is likely to complete, the study as planned.

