# 8.2 Exclusion Criteria (Treatment Cohort Only)

- 1. Prematurely discontinued LUM/IVA treatment in Study 115B.
- 2. History of any comorbidity or laboratory abnormality that, in the opinion of the investigator, might confound the results of the study or pose an additional risk in administering LUM/IVA to the subject (e.g., cirrhosis with portal hypertension).
- 3. History of drug intolerance or other serious reactions to LUM/IVA in Study 115B that would pose an additional risk to the subject in the opinion of investigator, and which should be discussed with the Vertex medical monitor.
- 4. Subjects with a history of allergy or hypersensitivity to LUM/IVA.
- 5. Liver function test (LFT) abnormality meeting criteria for LUM/IVA treatment interruption at the completion of Study 115B, for which no convincing alternative etiology is identified.
- 6. QTc value at the completion of Study 115B that would pose an additional risk to the subject in the opinion of investigator, and which should be discussed with the Vertex medical monitor (e.g., remained above the threshold value [>45 msec from baseline or >500 msec] on

- repeated measurement or was noted on 2 or more occasions with no identified alternative etiology for the increased QTc).
- 7. History of poor compliance with LUM/IVA and/or procedures in Study 115B as deemed by the investigator.
- 8. Participation in an investigational drug trial (including studies investigating LUM and/or IVA) other than Study 115B. NOTE: participation in a non-interventional study is permitted (including observational studies, registry studies, and studies requiring blood collections without administration of study drug).

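### Section 8.1 gives no Observational Cohort route to children who want treatment but are barred by exclusions 2 to 8, although the synopsis includes them

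*Protocol*

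**What the plan says.** The synopsis (Study Population, Observational Cohort) describes children who had at least 4 weeks of treatment in Study 115B and the required 115B visits, "but do not meet eligibility criteria for enrollment in the Treatment Cohort or who choose not to enroll in the Treatment Cohort". Ineligibility and choice are separate ways in.

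Section 8.1 says that subjects entering this cohort "must meet 1 of the following criteria" and lists three, numbered here in their order:

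- Route 1: "Completed 24 weeks of LUM/IVA treatment and the Safety Follow-up Visit in Study 115B, but do not want to enroll in the Treatment Cohort".
- Route 2: at least 4 weeks of treatment and the required visits, but at Week 24 the child is off drug "because of a drug interruption and either did not receive Vertex approval to enroll in the Treatment Cohort or do not want to enroll".
- Route 3: "Permanently discontinued LUM/IVA in Study 115B after receiving at least 4 weeks of treatment", with the child staying in 115B through Week 24 and any required follow-up visit.

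Section 8.2 lists eight exclusions and applies them to the Treatment Cohort only. They include "Prematurely discontinued LUM/IVA treatment in Study 115B" (exclusion 1), "History of drug intolerance or other serious reactions to LUM/IVA in Study 115B" (exclusion 3, where the investigator sees added risk) and "Liver function test (LFT) abnormality meeting criteria for LUM/IVA treatment interruption at the completion of Study 115B" (exclusion 5, where no convincing alternative cause is found). Exclusion 6 concerns QTc at the end of 115B, exclusion 7 poor compliance and exclusion 8 participation in another drug trial.

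**The concern.** The opening of Section 8 makes the inclusion criteria binding, so a site will work from Section 8.1. That section keeps the synopsis's choice route for completers but drops the ineligibility route. Ineligibility survives only in two special cases: interruption without sponsor approval (route 2) and permanent discontinuation (route 3).

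At stake is SAE follow-up after exposure in a study whose objective is long-term safety. A completer whose family declines treatment is followed for SAEs to Week 96. A completer whose family wants treatment, but who is barred because of a liver, QTc or intolerance finding, is not. A site that follows the synopsis would enroll this child, and a site that follows Section 8.1 would turn the child away. Because Section 8.2 is headed as applying to the Treatment Cohort only, its exclusions were evidently not meant to keep a child out of observation. Combined with the wording of Section 8.1, they do.

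**Working it through.** **The plan's own figure.** Section 12.1 expects 56 × (1 − 0.10) = 50.4, stated as 50, subjects to enroll. It reproduces, but nothing below depends on it.

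**Logic check.** Take children with at least 4 weeks of treatment who made the required 115B visits. Cross four facts:

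- status at Week 24 (on drug, interrupted, permanently discontinued);
- whether the family wants treatment;
- whether the sponsor approves (relevant only to interrupted children);
- whether any of exclusions 2 to 8 applies.

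The number of combinations is 2 × 2 = 4 on drug, 2 × 2 × 2 = 8 interrupted and 2 × 2 = 4 discontinued, 16 in all.

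| Week 24 status | Combinations | Treatment Cohort | Observational under both texts | Synopsis only, no 8.1 route |
|---|---|---|---|---|
| On drug | 4 | 1 | 2 | 1 |
| Interrupted | 8 | 1 | 6 | 1 |
| Discontinued | 4 | 0 | 4 | 0 |
| Total | 16 | 2 | 12 | 2 |

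The two combinations without a route are:

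- (a) on drug through Week 24, wants treatment, barred by an exclusion from 2 to 8. Route 1 fails because the family does want treatment. Routes 2 and 3 fail because there was no interruption or discontinuation.
- (b) interrupted at Week 24, sponsor approval given, wants treatment, barred by an exclusion from 2 to 8. Route 2 fails on both of its options. Route 1 fails on the family's wish, whether or not the child counts as having completed 24 weeks. Route 3 fails because the drug was not permanently stopped.

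**Is there a route elsewhere?** Sections 9.1.1 and 9.1.3 cover timing and contacts and add none. SAP Sections 4 and 7.1 only refer back to the inclusion criteria.

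**Which exclusions produce the gap.** Exclusion 1 does not, since route 3 takes those children after at least 4 weeks of treatment. Exclusions 5 and 6 can, because they look at findings at the completion of 115B. Section 12.2 mentions a planned 2-week washout in 115B, so a finding first seen at the end can arise in a child who never interrupted or stopped. Exclusion 3 can, if the intolerance did not stop dosing. Exclusions 7 and 8 open the same gap for reasons unrelated to safety, and exclusion 2 does so in part, since it also covers conditions that might only confound the results.

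**Follow-up lost per child.** 96 weeks × 7 = 672 days, and 672 / 365.25 = 1.84 years. This is a maximum, because Section 9.1.3 ends participation when a child moves to commercial drug. The total is at most 1.84 years times the number of children in the gap, and the documents do not give that number.

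**The case against.** The best case on the other side accepts that the texts differ but holds that little follows. Most of it stands as a limit on scope.

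A reader might infer that every child with a liver, QTc or intolerance signal loses follow-up. The documents do not support that. Route 2 admits any child off drug at Week 24 through interruption who lacks sponsor approval, and route 3 admits those who stopped permanently after at least 4 weeks and stayed for the visits. The liver rules in Section 11.6.3 of this protocol require interruption at set thresholds, and discontinuation if no other cause is found. If 115B used the same rules, many children meeting exclusion 5 would enter by routes 2 or 3. The 115B rules are not in the documents, and findings first seen at the end of 115B would still fall in the gap.

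A reader might also infer that the primary safety result is distorted. It is not. SAP Section 10.5 places the primary objective in the Treatment Cohort. The Observational Cohort receives no study drug, has two telephone contacts after Day 1, collects SAEs only and is reported in listings.

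It is tempting, too, to size the gap against the difference 56 − 50 = 6 in Section 12.1. Those 6 are assumed 115B dropouts not expected to enroll in Study 116. They are not a forecast of the Observational Cohort and cannot serve as a denominator.

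Two further points carry less weight. A site could record a barred family as not wanting treatment, but that would misstate the facts and the text does not provide for it. Study 115B may have had its own later SAE reporting. The documents do not describe it, so the loss claimed here is of Study 116 follow-up only.

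**Conclusion.** The contradiction is real but narrow. As Section 8.1 stands, two kinds of child belong to the synopsis's Observational Cohort and can enter neither cohort: the completer, and the sponsor-approved interrupted child, whose families want treatment and who are barred by exclusions 2 to 8. Some of them are barred by a safety finding and others for unrelated reasons.

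The cost is up to 96 weeks of SAE collection per child. No count or percentage can be defended from the documents. No Treatment Cohort summary changes. What changes is who appears in the Observational Cohort listings, and whether sites apply one rule. The conclusion rests on reading the three routes literally and on the synopsis stating the intended cohort, which the heading of Section 8.2 supports.

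**What to change.** Reconcile Section 8.1 with the synopsis by adding Treatment Cohort ineligibility to two routes:

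- Route 1: admit a child who completed 24 weeks and the 115B Safety Follow-up Visit and who either fails the Treatment Cohort eligibility criteria or does not want to enroll in it.
- Route 2: list failing those criteria as a third option beside lack of sponsor approval and unwillingness.

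Both edits are needed. A change to route 1 alone may leave out the interrupted, sponsor-approved child, who may not count as having completed 24 weeks. Route 3 can stay as it is.

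The cost is a short protocol amendment and, for each added child, one Day 1 visit and two telephone contacts of a kind the study already runs. The SAP needs no change, since its listings already cover everyone enrolled in the Observational Cohort.
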